8.2 Responsibility for Analyses/In-House Blinding

The statistical analysis of the data obtained from this study will be the responsibility of the Clinical Biostatistics department of the SPONSOR.

The Sponsor will generate the randomized allocation schedule(s) for study treatment assignment for this protocol, and the randomization will be implemented in IVRS.

Although the trial is open label, analyses or summaries generated by randomized treatment assignment, actual treatment received, and/or PD-L1 biomarker status will be limited and documented. Further documentation will be provided in the sSAP. In addition, the CAC central review will be performed without knowledge of treatment group assignment.

Treatment-level results at the interim PFS analysis will be provided by the external unblinded statistician to the DMC. Key enrollment metrics and study data will also be monitored by the external unblinded statistician to inform the timing of the interim PFS. Limited additional SPONSOR personnel may be unblinded to the treatment level and/or PD-L1 biomarker results of the first PFS analyses, if required, in order to act on the recommendations of the DMC or facilitate regulatory filing after the PFS analysis. The extent to which individuals are unblinded with respect to results of interim analyses will be documented by the unblinded statistician.

The DMC will serve as the primary reviewer of the unblinded results of the PFS analyses and will make recommendations for discontinuation of the study or modification to an executive oversight committee of the SPONSOR. Depending on the recommendation of the DMC, the Sponsor may prepare a regulatory submission. If the DMC recommends modifications to the design of the protocol or discontinuation of the study, this executive oversight committee

may be unblinded to results at the treatment level in order to act on these recommendations. Additional logistical details, revisions to the above plan and data monitoring guidance will be provided in the DMC Charter.

8.3 Hypotheses/Estimation

Objectives and hypotheses of the study are stated in Section 3.0.

8.4 Analysis Endpoints

8.4.1 Efficacy Endpoints

Primary

Progression-free survival (PFS) – the International Myeloma Working Group response criteria (IMWG 2011) by **CAC blinded central review**

PFS is defined as the time from randomization to the first documented disease progression per IMWG 2011 based on CAC blinded central review or death due to any cause, whichever occurs first. See Section 8.6.1 for definition of censoring.

Secondary

Overall Survival (OS) OS is defined as the time from randomization to death due to any cause. Subjects without documented death at the time of the final analysis will be censored at the date of the last follow-up.

Overall Response Rate (ORR) – the International Myeloma Working Group response criteria (IMWG 2011 criteria) for partial, or better, responses by **CAC blinded central review**.

ORR is defined as the proportion of the subjects in the analysis population who achieved at least a partial response (CR+VGPR+PR) according to the IMWG 2011.

Duration of Response (DOR) – the International Myeloma Working Group response criteria (IMWG 2011) by **CAC blinded central review**.

For subjects who demonstrated at least a partial response, response duration is defined as the time from first documented evidence of at least a partial response until disease progression or death. Response duration for subjects who have not progressed or died at the time of analysis will be censored at the date of their last assessment.

Disease Control Rate (DCR) - the International Myeloma Working Group response criteria (IMWG 2011) for at least a partial response by **CAC blinded central review**.

Disease control rate is defined as the percentage of subjects who have achieved confirmed CR, VGPR, PR, or have demonstrated SD for at least 12 weeks prior to any evidence of progression.

Second Progression Free Survival (PFS2) - the time from randomization to subsequent disease progression after initiation of new anti-cancer therapy, or death from any cause, whichever occurs first, **by investigator assessment**.

8.4.2 Safety Endpoints

Safety measurements are described in Section 4.2.3.3.

8.5 ANALYSIS POPULATIONS

8.5.1 Efficacy Analysis Populations

The Intention-to-Treat (ITT) population will serve as the population for primary efficacy analysis. All randomized subjects will be included in this population. Subjects will be included in the treatment group to which they are randomized. Details on the approach to handling missing data are provided in Section 8.6.1 Statistical Methods for Efficacy Analyses.

8.5.2 Safety Analysis Populations

The All Subjects as Treated (ASaT) population will be used for the analysis of safety data in this study. The ASaT population consists of all randomized subjects who received at least one dose of study treatment. Subjects will be included in the treatment group corresponding to the study treatment they actually received for the analysis of safety data using the ASaT population. For most subjects this will be the treatment group to which they are randomized. Subjects who take incorrect study treatment for the entire treatment period will be included in the treatment group corresponding to the study treatment actually received. Any subject who receives the incorrect study medication for one cycle but receives the correct treatment for all other cycles will be analyzed according to the correct treatment group and a narrative will be provided for any events that occur during the cycle for which the subject is incorrectly dosed.

At least one laboratory or vital sign measurement obtained subsequent to at least one dose of study treatment is required for inclusion in the analysis of each specific parameter. To assess change from baseline, a baseline measurement is also required.

Details on the approach to handling missing data for safety analyses are provided in Section 8.6.2 Statistical Methods for Safety Analysis.

8.6 STATISTICAL METHODS

8.6.1 Statistical Methods for Efficacy Analyses

This section describes the statistical methods that address the primary and secondary objectives. Methods related to exploratory objectives and exploratory endpoints will be described in the supplemental statistical analysis plan (sSAP), this includes the ePRO data described in 7.1.2.9 and minimum residual disease (MRD). In addition, a separate SAP will describe the analysis of PK data described in Section 7.1.3.2

Efficacy results that will be deemed to be statistically significant after consideration of the Type I error control strategy are described in Section 8.7 Interim Analysis and Section 8.8, Multiplicity. Nominal p-values will be provided for other efficacy analyses but should be interpreted with caution due to potential issues of multiplicity.

Progression-free Survival (PFS)

The non-parametric Kaplan-Meier method will be used to estimate the PFS curve in each treatment group. A stratified Cox proportional hazards model with Efron's method of tie handling will be used to assess the magnitude of the treatment difference (i.e., hazard ratio) between the treatment arms. The hazard ratio and its 95% confidence interval from the stratified Cox model with Efron's method of tie handling and with a single treatment covariate will be reported. Age and ISS stage will be used as the stratification factors in both the stratified log-rank test and the stratified Cox model. The test of the primary hypothesis will be assessed by evaluation of the treatment difference in PFS using the stratified log-rank test.

Since disease progression is assessed periodically, PD can occur any time in the time interval between the last assessment where PD was not documented and the assessment when PD is documented. For the primary analysis, for the subjects who have PD, the true date of disease progression will be approximated by the date of the first assessment at which PD is objectively documented per IMWG 2011, regardless of discontinuation of study drug. Death is always considered as a confirmed PD event. Subjects without documented PD/death will be censored at the last disease assessment date.

In order to evaluate the robustness of the primary endpoint PFS per IMWG 2011 criteria by CAC blinded central review, we will perform two sensitivity analyses with a different set of censoring rules. The first sensitivity analysis is the same as the primary analysis except that it censors at the last disease assessment without PD when PD or death is documented after more than one missed disease assessment. The second sensitivity analysis is the same as the primary analysis except that it considers discontinuation of treatment or initiation of an anticancer treatment subsequent to discontinuation of study-specified treatments, whichever occurs later, to be a PD event for subjects without documented PD or death. The censoring rules for primary and sensitivity analyses are summarized in [Table 15](#) below. In case there are imbalances between treatment groups in disease assessment schedules or censoring patterns, additional PFS sensitivity analyses may be performed as supportive analyses, for

example: 1) A PFS analysis using time to scheduled disease assessment visit from randomization as opposed to actual disease assessment time; and, 2) Finkelstein’s (1986) likelihood-based score test [51] for interval-censored data, which modifies the Cox proportional hazards model for interval censored data in which the interval will be constructed so that the left endpoint is the date of the last disease assessment without documented PD and the right endpoint is the date of documented PD or death, whichever occurs earlier.

Table 15 Censoring Rules for Primary and Sensitivity Analyses of PFS

Situation	Primary Analysis	Sensitivity Analysis 1	Sensitivity Analysis 2
No PD and no death; new anticancer treatment is not initiated	Censored at last disease assessment	Censored at last disease assessment	Censored at last disease assessment if still on study therapy; progressed at treatment discontinuation otherwise
No PD and no death; new anticancer treatment is initiated	Censored at last disease assessment before new anticancer treatment	Censored at last disease assessment before new anticancer treatment	Progressed at date of new anticancer treatment
PD or death documented after ≤ 1 missed disease assessment	Progressed at date of documented PD or death	Progressed at date of documented PD or death	Progressed at date of documented PD or death
PD or death documented after ≥ 2 missed disease assessments	Progressed at date of documented PD or death	Censored at last disease assessment prior to the ≥ 2 missed disease assessment	Progressed at date of documented PD or death

The proportional hazards assumption of the Cox model will be examined using both graphical and analytical methods for the primary PFS analysis. The log[-log] of the survival function vs. time for PFS will be plotted for each treatment arm. If the curves are not parallel, indicating that hazards are not proportional, supportive analyses may be conducted to account for the possible non-proportional hazards effect associated with immunotherapies, for example, using Restricted Mean Survival Time (RMST) method [52], parametric method etc. Details will be described in supplemental SAP.

The common hazard ratio across strata assumption will be examined using the two-step approach of Mehrotra et al. [53]. In this method, the HR will first be estimated separately for each stratum using an unstratified Cox model and then the stratum specific estimates will be combined into an overall estimate using a weighted approach. Details will be described in the supplemental SAP.

Overall Survival (OS)

The non-parametric Kaplan-Meier method will be used to estimate the survival curves. A stratified Cox proportional hazards model with Efron's method of tie handling will be used to assess the magnitude of the treatment difference (i.e., the hazard ratio). The hazard ratio and

its 95% confidence interval from the stratified Cox model with a single treatment covariate will be reported. Age and ISS stage will be used as the stratification factors in both the stratified log-rank test and the stratified Cox model. The test of the OS hypothesis will be assessed by evaluation of the treatment difference in OS using the stratified log-rank test.

Exploratory analyses to adjust for the effect of subsequent lines of therapy on OS may be performed based on recognized methods (e.g., the Rank Preserving Structural Failure Time (RPSFT) model proposed by Robins and Tsiatis (1989) [54], two-stage model, etc. The choice of the method will be based on an examination of the appropriateness of the data to the assumptions required by the method. Further details of sensitivity analyses will be described in supplemental SAP.

Overall Response Rate (ORR)

The stratified Miettinen and Nurminen's method based on sample size weighting will be used for comparison of the ORR between the treatment groups. A 95% confidence interval for the difference in response rates between the active arms and the standard therapy arm will be provided. Age and ISS stage will be used as the stratification factors in the analysis.

Duration of Response (DOR)

Response duration will be summarized descriptively using Kaplan-Meier medians and quartiles, results permitting. Only the subset of subjects who achieve at least a partial response will be included in this analysis.

Disease Control Rate (DCR)

The stratified Miettinen and Nurminen's method based on sample size weighting will be used for comparison of the DCR between the treatment groups. A 95% confidence interval for the difference in DC rates between the active arms and the standard therapy arm will be provided. Age and ISS stage will be used as the stratification factors in the analysis.

Second Progression-free Survival (PFS2)

The non-parametric Kaplan-Meier method will be used to estimate the PFS2 curves. The treatment difference in PFS2 will be assessed by the stratified log-rank test. A stratified Cox proportional hazards model with Efron's method of tie handling will be used to assess the magnitude of the treatment difference (i.e., the hazard ratio). The hazard ratio and its 95% confidence interval from the stratified Cox model with a single treatment covariate will be reported. Age and ISS stage will be used as the stratification factors in both the stratified log-rank test and the stratified Cox model.

Further details of PFS2 analyses will be described in supplemental SAP.

Table 16 summarizes the primary analysis approach for primary and secondary efficacy endpoints. Sensitivity analysis methods are described above for each endpoint.

Table 16 Analysis Strategy for Primary and Secondary Efficacy Endpoints

Endpoint/Variable (Description, Time Point)	Statistical Method†	Analysis Population	Missing Data Approach
Primary Endpoint			
PFS per IMWG 2011 by CAC blinded central review	Testing: Stratified Log-rank test. Estimation: Stratified Cox model with Efron's tie handling method	ITT	
 • Primary censoring rule • Sensitivity analysis 1 • Sensitivity analysis 2 (details in Table 15)
Secondary endpoints			
OS	Testing: Stratified Log-rank test Estimation: Stratified Cox model with Efron's tie handling method	ITT	Censored at last date known alive
ORR per IMWG 2011 by CAC blinded central review	Stratified Miettinen and Nurminen method	ITT	Subjects with missing data are considered non-responders
DOR per IMWG 2011 by CAC blinded central review	Summary statistics using Kaplan-Meier method	All responders in ITT	Censored at last assessment date if responding at the time of analysis
DCR per IMWG 2011 by CAC blinded central review	Stratified Miettinen and Nurminen method	ITT	Subjects with missing data are considered as disease not under control.
PFS per investigator assessment	Testing: Stratified Log-rank test. Estimation: Stratified Cox model with Efron's tie handling method	ITT	Details to be provided in sSAP
† Statistical models are described in further detail in the text. For stratified analyses, Age and ISS stage will be used as the stratification factors in the stratified log-rank test, stratified Cox model and stratified Miettinen and Nurminen test.			

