7.1.5.5 Efficacy Follow-up Visits

Subjects who discontinue trial treatment for a reason other than confirmed disease progression will move into the Follow-Up Phase to monitor disease status and should be assessed every 4 weeks (\pm 7 days) until (1) the start of new anti-cancer treatment, (2) documented disease progression, (3) death, (4) withdraw of consent or (5) the end of the trial, whichever occurs first. The Sponsor may request survival status to be assessed at additional time points during the course of the study (not to exceed approximately 12 weeks). Every effort should be made to collect information regarding disease response assessment in the follow-up period. Prior to discontinuing patients from therapy, consult with Sponsor and

submit the Treatment Termination & Disease Assessment Termination Form. NOTE: For both groups, if either pembrolizumab, lenalidomide, or low dose dexamethasone is discontinued due to unacceptable toxicity, subjects can continue to receive study treatment with the remaining study drugs without discontinuing from study.

Information regarding post-study anti-myeloma treatment will be collected if new treatment is initiated.

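### PFS Sensitivity Analysis 2 counts a treatment stop or switch as failure only if no PD or death is documented later, so it is not a coherent time-to-event definition

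*Combined protocol and SAP*

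**What the plan says.** Section 8.6.1 commits to two sensitivity analyses of the primary PFS endpoint. The second (SA2) follows the primary analysis, except that it takes treatment discontinuation or the start of subsequent anticancer therapy, "whichever occurs later, to be a PD event for subjects without documented PD or death".

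The SA2 column of Table 15 agrees with the text:

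- No PD, no death, no new therapy: "Censored at last disease assessment if still on study therapy; progressed at treatment discontinuation otherwise".
- No PD, no death, new therapy started: "Progressed at date of new anticancer treatment".
- PD or death documented, in both rows and whatever the number of missed assessments: "Progressed at date of documented PD or death".

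The last two rows make no exception for a subject who had already stopped or switched. The primary rule that SA2 inherits dates PD "regardless of discontinuation of study drug" and adds: "Death is always considered as a confirmed PD event".

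Follow-up continues after a stop. Section 7.1.5.5 says: "Subjects who discontinue trial treatment for a reason other than confirmed disease progression will move into the Follow-Up Phase to monitor disease status". Assessments there are 4-weekly. That section and 7.1.2.8.5 end disease assessment when new anticancer treatment starts. Section 5.8, by contrast, continues assessments to progression in subjects taken off study treatment because they received non-protocol therapy before progression. Section 7.1.5.5.1 collects survival after a switch.

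**The concern.** A time-to-event endpoint needs a failure date that is fixed by what has happened up to that date. SA2 looks forward. The same stop at month 6 is a failure at month 6 if nothing else is documented by the cutoff, and no failure at all if PD or death is documented later. This has two consequences.

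- **Inverted order.** Among subjects with the same stop date, the one observed to remain progression-free fails first, and the one who progresses or dies fails later.
- **Dates that move.** A failure recorded at one cutoff can be withdrawn and re-dated later at the next.

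SA2 is the only committed check that treats early stopping or switching as failure, in an open-label trial. If its failure times are not well defined, its hazard ratio and medians have no clear interpretation.

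**Working it through.** **The plan's own figure.** No figure is given for SA2. The nearest is 227 PFS events for 90% power at HR 0.65, one-sided 0.025: 4 × (1.960 + 1.282)² / (ln 0.65)² = 226.5, so 227. It reproduces. The point does not depend on it.

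**The rule on example records.** All times are months from the same start, with cutoff at month 30.

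| Record | SA2 as written | Earliest of all four events |
|---|---|---|
| Stop 6, no PD, no new therapy | 6 | 6 |
| Stop 6, new therapy 9, no PD | 9 | 6 |
| Stop 6, PD 14 | 14 | 6 |
| Stop 6, new therapy 9, death 25 | 25 | 6 |
| Stop at PD, month 14 | 14 | 14 |

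The fourth subject dies and gets 19 months more event-free time than the first (25 − 6). With a cutoff before month 25, that subject's SA2 date would be 9. The last row shows that stopping because of PD creates no conflict.

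**How many events are affected.** Inputs from section 8.9: 320 per arm, exponential PFS with control median 25.5 months, HR 0.65, 18 months of enrolment, 12 further months. Assumed: entry is uniform, so follow-up is uniform on 12 to 30 months; stopping without PD is exponential at rate μ, independent of PD.

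Let M(r) = (e^(−12r) − e^(−30r)) / (18r). Per arm:

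- PD or death after a stop = 320 × {[1 − M(λ)] − [λ/(λ+μ)] × [1 − M(λ+μ)]}
- SA2 events = 320 × [1 − M(λ+μ)]

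λ for Arm B is ln 2 / 25.5 = 0.02718, and for Arm A 0.65 × 0.02718 = 0.01767. With μ = 0.015 per month:

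- Arm A: 320 × {0.3072 − 0.5409 × 0.4891} = 98.3 − 84.7 = 13.6, of 156.5 SA2 events.
- Arm B: 320 × {0.4294 − 0.6444 × 0.5775} = 137.4 − 119.1 = 18.3, of 184.8.
- Total: about 32 of 341 (9%).

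The same formula gives 22 of 310 (7%) at μ = 0.01 and 58 of 418 (14%) at μ = 0.03. By simulation, the mean delay at 0.015 is about 7.5 months. If the PD/death hazard is assumed to double after a stop, the count at 0.015 is 54 of 341 (16%). At 0.03 in Arm A and 0.015 in Arm B with doubling it is 74 of 383 (19%).

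These counts assume PD is still collected after new therapy. With only deaths counted from that point (OS hazard from section 8.9), they fall to about 23 of 341 in the equal case and 56 of 384 in the last case.

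**Effect on the hazard ratio.** Simulation with 640 subjects, cutoff at month 30, 400 runs per scenario, stopping independent of PD and no new therapy modelled:

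| Stop per year, A / B | SA2 as written | Earliest-of | Re-dated events |
|---|---|---|---|
| 10% / 10% | 0.735 | 0.735 | 19 of 302 |
| 20% / 20% | 0.797 | 0.793 | 38 of 363 |
| 20% / 10% | 0.988 | 0.998 | 28 of 335 |
| 30% / 15% | 1.146 | 1.161 | 41 of 379 |
| 30% / 10% | 1.293 | 1.319 | 35 of 365 |
| 10% / 20% | 0.587 | 0.579 | 30 of 328 |

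The number of SA2 events is the same under both rules; only dates move. With doubled hazard after stopping, and 60% starting new therapy a mean of 3 months later, monthly rates of 0.03 v 0.015 give 1.09 v 1.13 (Arm A median 16.7 v 14.6 months). Rates of 0.04 v 0.015 give 1.30 v 1.37 (14.7 v 12.0 months).

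**The case against.** **SA2 may not be meant as time to first failure.** The text presents it as a change of censoring rules, and Table 16 lists it under missing data. On that view SA2 replaces censoring by failure as a penalty and leaves observed events at their true dates. This describes the text fairly but does not rescue the rule. A subject who stops at month 6 and is then seen to be progression-free every 4 weeks has no missing outcome, yet is "progressed at treatment discontinuation otherwise". A subject under the same follow-up whose PD is seen later keeps the later date.

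**An earliest-of rule interacts with the clinical hold.** Every subject still on treatment was made to stop. A literal earliest-of rule would fail all of them at that stop, and their later PD or deaths would no longer set the SA2 date. This stands, and the fix has to deal with it.

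**The plan leaves room to adapt.** Section 8.6.1 allows further PFS sensitivity analyses if censoring is imbalanced, and section 8.0 says the analysis may be modified because of the study's status. Both are optional, and neither states a different SA2 rule.

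**Stronger readings that a reader might infer.**

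- *The rule favours pembrolizumab.* The documents give no stopping rates, and the shift favours whichever arm stops more. At 10% v 20% a year the written rule is slightly less favourable to pembrolizumab (0.587 v 0.579). Sections 5.2.1.1 and 5.8 also let a subject drop one toxic drug and continue the others, so pembrolizumab toxicity need not end treatment.
- *SA2 would hide a lack of robustness.* Where Arm A stops more, both versions move far from the design HR of 0.65 and would be read the same way.
- *Worse outcomes always get later dates.* This holds only for subjects with the same stop date whose PD or death follows the stop.

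**Conclusion.** The point holds as a defect of definition. SA2 decides whether a stop or switch is a failure by what is documented afterwards, so failure order can invert among subjects with the same stop date, and failure dates depend on the cutoff.

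Its numerical size is modest and rests on assumed stopping rates, and in the larger cases on an assumed doubling of hazard after stopping. Roughly 7% to 19% of SA2 events are affected for monthly rates of 0.01 to 0.03, fewer where PD is not collected after new therapy. The SA2 hazard ratio changes by less than 0.01 with equal stopping. In the unequal scenarios it changes by about 0.01 to 0.04, and by 0.07 at 0.04 v 0.015 per month. The shift favours the arm that stops more, which is towards 1 except where the ratio is already close to 1 (0.988 v 0.998).

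SA2 is supportive and carries no alpha. The primary PFS test and its type I error are not touched. The change is worth making because it is cheap and gives the analysis a meaning.

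**What to change.** In section 8.6.1 and in the SA2 column of Table 15:

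- Date the SA2 event, for every subject, at the earliest of documented PD, death, treatment discontinuation and start of new anticancer treatment. Censor at the last disease assessment only if none has occurred. Remove the restriction to subjects without PD or death, and the choice of the later date.
- At minimum, cap the two PD-or-death rows at the date that the first two rows would give. In the examples, stop 6 with PD 14 becomes 6, and stop 6, new therapy 9, death 25 becomes 9.
- State that discontinuation forced solely by the 03-JUL-2017 clinical hold is not an SA2 failure, and say how new therapy begun after such a stop is treated. Section 8.6.3 already plans to display the primary reason for discontinuation, which can support this.

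The cost is a few lines of wording and a changed derivation, with no new data. SA2 event-free times become shorter, and later PD or death no longer sets the SA2 date in subjects who had already stopped. Those later events keep their role in the primary analysis. Leaving out hold-only stops lowers the SA2 event count; the re-dating itself does not change it.

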8.0 STATISTICAL ANALYSIS PLAN

This section outlines the statistical analysis strategy and procedures for the study. If, after the study has begun, changes made to primary and/or key secondary hypotheses, or the statistical methods related to those hypotheses, then the protocol will be amended (consistent with ICH Guideline E-9). Changes to exploratory or other non-confirmatory analyses made after the protocol has been finalized, but prior to the conduct of any analysis, will be documented in a supplemental SAP (sSAP) and referenced in the Clinical Study Report (CSR) for the study. A separate PK analysis plan as well as biomarker analysis plan will be provided. Post hoc exploratory analyses will be clearly identified in the CSR. The PRO analysis plan will also be included in the sSAP.

On 03-JUL-2017, the US FDA placed KN183, KN185 and cohort 1 of KN023 on clinical hold based on safety data from KN183 and KN185 presented to the DMC. The FDA determined that the risks of pembrolizumab plus pomalidomide or lenalidomide outweighed any potential benefit for patients with multiple myeloma. Based on this decision, the treatment phase of KN183 and KN185 is closed effective immediately. All subjects must stop study treatment, complete the Discontinuation Visit and move into the long-term safety and survival follow-up per protocol.

Due to the current status of the study the statistical analysis of this section may be modified and will be reported in the CSR.

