Interim PFS Analysis	All subjects enrolled and ~ 115 PFS events are observed (~ 20 months after trial starts)	PFS: pembrolizumab in combination with SOC vs. SOC	HR at bound p value (1-sided)	~0.54 ≤ 0.0004	~0.99 ≥ 0.48
Final PFS Analysis:	PFS analysis and ~227 PFS events are observed (~30 months after trial starts)	PFS: pembrolizumab in combination with SOC vs. SOC	HR at bound p value (1-sided)	~0.77 ≤ 0.0249	Not applicable
OS analysis	OS Events: - Overall: 195 (~56 months after trial starts)	OS: pembrolizumab in combination with SOC vs. SOC	HR p value (1-sided)	~0.76 ≤ 0.025	Not applicable

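### With a PFS cutoff after the 03-JUL-2017 hold, Sensitivity Analysis 2 counts hold-forced treatment stops as progression, and a true hazard ratio of 0.65 reads about 0.9 or higher

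*Combined protocol and SAP*

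**What the plan says.** Section 8.6.1 offers two sensitivity analyses as checks on the robustness of primary PFS. In the second (SA2), Table 15 handles a subject with no progression, no death and no new anticancer treatment as "Censored at last disease assessment if still on study therapy; progressed at treatment discontinuation otherwise". If new treatment has started, the entry is "Progressed at date of new anticancer treatment". The text gives the same rule: it takes treatment discontinuation or later anticancer treatment, "whichever occurs later, to be a PD event for subjects without documented PD or death". Neither place distinguishes reasons for stopping.

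Section 8.0 records the hold of 03-JUL-2017 and instructs: "All subjects must stop study treatment, complete the Discontinuation Visit and move into the long-term safety and survival follow-up per protocol". It then adds: "Due to the current status of the study the statistical analysis of this section may be modified and will be reported in the CSR". The same section sends "Changes to exploratory or other non-confirmatory analyses made after the protocol has been finalized" to a supplemental SAP, provided they precede any analysis. No replacement rule for Table 15 is given. Amendments 06, 07 and 08 all postdate the hold.

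Two other places bear on the consequence. Table 18 (section 8.7.1) forecasts the final PFS analysis for about 30 months after trial start. Section 7.1.5.5 says subjects who stop for a reason other than confirmed progression "will move into the Follow-Up Phase to monitor disease status and should be assessed every 4 weeks".

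**The concern.** SA2 assumes that stopping treatment without documented progression may hide a treatment failure. The hold breaks that assumption. It stopped everyone on one calendar date, in both arms, for a reason unrelated to the subject's disease. After that date nobody is still on study therapy, so the censoring branch of the rule is empty. For a subject on treatment at the hold who never progresses, dies or starts new therapy, the event time is simply the time from randomization to the hold. Randomization makes that time alike in the two arms.

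The result is a hazard ratio pulled towards 1. A real benefit would look fragile, a real harm would look smaller, and a genuine difference between arms in early stopping, which this rule exists to show, would be diluted.

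There is a second effect if disease assessment continues after the hold. A subject who never progresses is dated at the hold, while one who progresses later is dated at that later progression. The arm with fewer progressions then collects more early events, which can push the ratio above 1.

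**Working it through.** **Inputs from the plan (section 8.9).** 640 subjects, 1:1; 18-month enrollment; exponential PFS with control median 25.5 months; hazard ratio 0.65; dropout 2% at one year. **Assumed:** uniform entry; hold at month 16 to 23 after start; share starting new therapy after the hold, 0–80%.

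**The plan's own figure.** Events = 4(1.960 + 1.282)² / (ln 0.65)² = 42.03 / 0.1856 = 226.5, so 227, as stated. Under uniform entry the model expects 232 PFS events at month 30, close to Table 18. At month 20 it expects 134 against the plan's approximate 115, so accrual length was also varied.

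**When the hold fell.** The original protocol is dated 28-JUL-2015. From there to 03-JUL-2017 is 706 days; 706 / 30.44 = 23.2 months. The hold therefore came at most 23.2 months after start, and month 30 lies at least 30 − 23.2 = 6.8 months after it.

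**Hand calculation, hold at month 20, cutoff just after it, dropout ignored.** Follow-up at the hold is uniform on 2 to 20 months. The share still event-free is [exp(−2λ) − exp(−20λ)] / (18λ).
- Control: λ = ln 2 / 25.5 = 0.02718; share 0.749; 320 × 0.749 = 240.
- Pembrolizumab: λ = 0.65 × 0.02718 = 0.01767; share 0.827; 320 × 0.827 = 265.

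About 505 of 640 subjects (79%) become SA2 events only because of the hold, against about 135 true PFS events.

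**Simulation with dropout (1,200–3,000 trials per scenario, unstratified Cox), true hazard ratio 0.65, cutoff just after the hold:**

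| Hold month | True PD/death | Hold-caused events | SA2 HR as written | Control median as written (months) |
|---|---|---|---|---|
| 16 (568 enrolled) | 90 | 472 (83%) | 0.935 | 6.4 |
| 18 | 112 | 520 (81%) | 0.926 | 6.9 |
| 20 | 134 | 496 (77%) | 0.912 | 8.5 |
| 23 | 166 | 461 (72%) | 0.895 | 10.7 |

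On the same data primary PFS reads 0.647–0.651, and SA2 with a hold exception reads 0.668–0.672. With the cutoff one day before the hold there are no hold-caused events and SA2 reads 0.665–0.670.

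**Cutoff at month 30, hold at month 16/18/20/23:**

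| Disease assessment after hold | New therapy | SA2 HR |
|---|---|---|
| Continues | none | 1.024 / 0.998 / 0.970 / 0.924 |
| Continues | 80%, 1.5 months after hold | 0.952 / 0.936 / 0.918 / 0.894 |
| Ended at hold | none | 0.934 / 0.928 / 0.913 / 0.896 |
| Ended at hold | 80%, 1.5 months after hold | 0.921 / 0.918 / 0.906 / 0.884 |

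**Independent rerun (400,000 subjects per scenario, dropout ignored).** Over varied cutoffs, accrual lengths of 9 to 23 months and new-therapy rates, SA2 reads about 0.87 to 1.05. For a single trial of 640 with the hold at month 20 and cutoff at the hold, the mean is 0.92 (95% range 0.78–1.06).

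**Other true effects, cutoff just after the hold.** 0.80 reads 0.94–0.96; 1.00 reads 1.00–1.01; 1.30 reads 1.06–1.09.

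**Differential stopping (illustrative rates).** With 1% per month stopping in control, 2% in the pembrolizumab arm and a true PFS ratio of 1.00, SA2 reads 1.24–1.26 with the exception and 1.07–1.10 as written.

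**The case against.** The best reply is that SA2 is built to count non-progression stops, so it reads nearer 1 than primary PFS even without a hold. The base simulation has almost no ordinary stops, so the contrast of 0.67 with 0.9 overstates the hold's share. That part stands. With ordinary non-differential stops assumed at 15% per year and the cutoff at the hold, SA2 reads 0.76–0.77 with the exception and 0.91–0.93 as written. At 30% per year the figures are 0.83–0.84 and 0.92–0.94. The gap due to the hold shrinks to 0.14–0.17 and 0.08–0.11. The as-written reading stays above 0.9 in each case.

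Other points stand in part:
- Month 30 in Table 18 is a forecast for a trial that kept treating. It makes a post-hold cutoff likely but does not establish one.
- The supplemental SAP was not available and may contain the exception. The warning in section 8.0 that the analysis may change gives no rule, and in an open-label trial it leaves the choice open until results are known.
- The instruction to follow subjects per protocol, read with section 7.1.5.5, favors continued disease assessment after the hold. The rows that assume continuation are then the relevant ones; they reach further towards 1, and beyond.
- About 0.9 is not a floor; corner cases reach 0.87–0.88.
- SA2 carries no alpha and no decision rule, and it creates no false effect under a true ratio of 1. This limits the weight of the point without removing it.

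**Conclusion.** The concern holds and is worth fixing. Followed as written with a post-hold cutoff, SA2 mainly measures time from randomization to a stop common to both arms. A true ratio of 0.65 then reads about 0.9 or higher (0.87 to 1.05 across the scenarios), and a true 1.30 reads below 1.10 with a cutoff just after the hold. The size rests on the assumed hold month, uniform accrual, and assumed behavior after the hold. The defect depends on the cutoff, which the documents do not give. That the rule is stated without an exception is certain; how far it distorts the actual analysis cannot be settled from these documents. Only a supportive analysis is affected: primary PFS, alpha, power and Sensitivity Analysis 1 are untouched.

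**What to change.** Add to the SA2 column of Table 15 and its matching text, or to the supplemental SAP, a rule such as:

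*Discontinuation caused by the 03-JUL-2017 clinical hold, identified by recorded reason and stop date, and new anticancer therapy begun after such a discontinuation, are not PD events. These subjects follow the Primary Analysis column. All other discontinuations keep the current SA2 rule.*

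State the PFS data cutoff. In the CSR, report the rule as a change made after the hold; the as-written version can be shown beside it.

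The cost is one sentence and no new data. There are two drawbacks. It is a post-hold change in an open-label trial and must be labeled so. Hold stops will also have to be picked out largely by date, because section 5.8 lists no hold-specific reason, only a general administrative one. Censoring these subjects at the hold is an alternative and gives nearly the same result (0.66–0.68 for a true 0.65).
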